The **Data Monitoring and Ethics Committee (DMEC)** is also independent. The group will meet at least annually, with interim analysis reports from the UoSCTU, to give advice on continuing recruitment. A recommendation to discontinue recruitment (in all patients or in selected subgroups) will be made only if the result is likely to convince a broad range of investigators including participants in the trial and the general clinical community. If a decision is made to continue, the DMEC will advise on the frequency of future reviews of the data on the basis of accrual and event rates. The DMEC will make recommendations to the TSC as to the continuation of the trial.

25. Publication and intellectual property

All publications and presentations relating to the trial will be authorised by the TMG. The first publication of the trial results from all centres will be in the name of the TMG. Members of the TMG will be listed as authors and other significant contributors will be cited by name if published in a journal where this does not conflict with the journal policy. Surgeons and oncologists at the highest recruiting centres will also be acknowledged. The ISRCTN number allocated to this trial (ISRCTN22944367) will be attached to any publications resulting from this trial.

Participating centres may not publish trial results prior to the first publication by the TMG or without prior written consent from the TMG. Ownership of intellectual property resulting from the trial will be governed in accordance with the relevant agreements and the CRUK terms and conditions for research grants and awards.

26. Protocol amendments

Please check with UoSCTU that you are using the most recent version of the New EPOC clinical trial protocol.

The protocol was amended on the 16 January 2012 to update the analysis plan and statistics which resulted in reducing the sample size to 288 patients.

The protocol was amended on the 08 December 2010 to correct an administration error regarding infusion rates of subsequent doses of Cetuximab. Clarification was also made to information relating to chemotherapy delivery following Cetuximab infusion. An update was also made to the radiation risk assessment

The protocol was amended on 28 July 2010 to remove Capecitabine and permit first line use of Irinotecan as treatment options.

An amendment to the protocol was completed on 22 April 2009 to update the randomisation stratification factors. Patient information sheets, consent forms and GP information sheets were also removed from the appendices.

The protocol was amended on 16 September 2008 to offer Irinotecan and Fluorouracil based chemotherapy to patients previously treated with Oxaliplatin.

The protocol was amended on 4 July 2008 to introduce kRAS genotyping for all patients, in order to exclude patients with a confirmed kRAS-mutant genotype in the primary cancer from the trial due to a lack of efficacy of Cetuximab in this patient group (data presented at ASCO 2008).

The protocol was amended on 14 March 2008 to change the formulation of Cetuximab used in this trial from 2 mg/ml to 5 mg/ml.

A minor amendment to the protocol was completed on 16 January 2008, to update the randomisation stratification factors.

The protocol was amended on 3 January 2008 to clarify the study treatment regimens, tissue bank details, and other items to ensure efficient management of the trial.

The protocol was amended on 24 July 2007 to reduce the dose of Capecitabine from 1000 to 850 mg/m² in subjects receiving CAPOX + Cetuximab following an interim analysis of the COIN trial where a significantly increased prevalence of grade 3/4 diarrhoea was shown with this regimen. Additional information was included in the Appendix to describe the dose adjustments to be followed for subjects with diarrhoea.

This protocol was amended on the 11 October 2017 to amend the end of study date and correct changes to study personnel both at the University of Southampton CTU and the Trial TMG.

27. References

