This protocol has been evaluated in a large phase III trial including patients with metastatic colorectal cancer¹². Please see appendices I-IV for details of the chemotherapy regimens.

5. Aims

The **primary aim** of the New EPOC trial is to determine whether the addition of Cetuximab to Oxaliplatin plus modified de Gramont or Irinotecan plus modified de Gramont combination chemotherapy results in improved progression free survival when compared with combination chemotherapy alone in patients who do not possess a kRAS mutant genotype confirmed by laboratory analysis.

Secondary aims

1. To evaluate overall survival.
2. To evaluate quality of life.
3. To compare the experimental arm in terms of cost effectiveness in a UK treatment setting
4. To determine whether the addition of Cetuximab to combination chemotherapy as above results in improved progression free survival when compared with combination chemotherapy alone in patients who possess the kRAS-wt genotype confirmed by laboratory analysis

Translational research aims

1. To assess the difference in progression free survival with chemotherapy plus Cetuximab for all patients irrespective of EGFR detectability in tumour tissue on IHC; for patients with detectable EGFR and for those with undetectable EGFR.
2. To determine, from DNA extracted from peripheral blood, the impact of individual variance in DNA repair capacity on tumour response, progression free survival and grade 3/4 toxicities.
3. To determine, from DNA extracted from peripheral blood, whether variance in the enzymes involved in the metabolism, transport and cellular targets of the drugs used affects tumour response, progression free survival and grade 3/4 toxicities.
4. To determine the effect of Cetuximab on the expression profile of hepatic metastases.

6. Outcome measures

Primary: progression-free survival.

Secondary: pre-operative response, pathological resection status, peri-operative safety findings, overall survival, EQ-5D, EORTC QLQ-C30, EORTC QLQ-LMC21, measures for cost effectiveness.

Definitions

Progression-free survival (PFS) is defined as the time from randomisation to first recurrence/disease progression or death, whichever occurs first. Patients not experiencing recurrence/progression/death will be censored at the date of the last follow-up examination. PFS will be assessed as follows:

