In patients with resected metastases (R0 or R1 or R2), PFS will be considered to be the time from randomisation to the first of the following events:

- Recurrence/disease progression after surgery
- Death

In patients with unresected metastases, PFS will be considered as the time from randomisation to the first of the following events:

- Disease progression (whenever it occurs, before or after the planned surgery date)
- Death

Overall survival is defined as the time interval between the date of randomisation and the date of death. Patients who are still alive when last traced will be censored at the date of last follow-up.

Pre-operative response: evaluation of the activity of study treatment on hepatic metastases will be done according to the RECIST criteria (see Appendix V), after the end of the pre-operative treatment period by abdominopelvic computed tomography (CT) scan or magnetic resonance imaging (MRI) ideally within 1 week but not longer than 2 weeks. As patients will undergo surgery

within 2 to 4 weeks of CT scanning at the end of the pre-operative period, the 4 week confirmation does not apply for patients who achieve their first response at this time point.

A pre-operative safety finding will be if >6 weeks delay of surgery due to study treatment-related toxicity, with the delay being measured between the end of pre-operative chemotherapy (last day of last cycle) and surgery.

Pathological resection rate: following surgery, the pathologist will assess the resection as R0, R1 or R2. The rates of R0, R1 and R2 resections will be presented.

Peri-operative safety findings: any of the following events provided they are due to a severe surgery-related complication (i.e. wound infection, intra-abdominal infection, severe sepsis.):

- Prolongation of hospitalisation (discharge >20 days after surgery)
- Re-hospitalisation within 30 days of surgery
- Re-operation under general anaesthesia within 30 days of surgery (excluding secondary surgery after R1 resection)
- Death during surgery or within 30 days of surgery
- Other severe pre- or post-operative complications within 30 days of surgery:
 - Surgery-associated bleeding with replacement ≥ 4 units of erythrocyte concentrates
 - Biliary fistula for more than 10 days with a discharge of >100 mL/day
 - Transient liver failure, defined as a bilirubin level >10 mg/dL lasting >7 days
 - Renal failure requiring dialysis

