- The ambulatory technique for OxMdG and IrMdG is described in AAppendix III. These regimens may also be given on an inpatient basis, but investigators are urged to use outpatient ambulatory treatment whenever possible.

9.b Treatment duration and breaks

- **Arm A (Control, OxMdG / IrMdG):** These patients will receive 12 weeks of pre-operative and 12 weeks of post-operative chemotherapy dependent on cumulative toxicity, post-surgical performance status or because of patient choice to stop chemotherapy. Patients in this arm should continue on treatment with no more than a three week interval off treatment for any reason although the post surgical interval can be 6 weeks. *The cumulative toxicity that is most likely to occur is the neuropathy associated with Oxaliplatin, which increases in incidence from about 12 weeks duration of therapy. If this occurs, patients may continue on the fluorouracil component of the regimen with dose increment as indicated in Appendix I.* If the neuropathy resolves to < grade 1 the Oxaliplatin may be reintroduced cautiously at the investigator's discretion.
- **Arm B: OxMdG / IrMdG plus Cetuximab:** These patients will receive chemotherapy as Arm A above plus Cetuximab. Patients in this arm should continue on treatment with no more than a three week interval off treatment for any reason although the post surgical interval can be 6 weeks. Cetuximab will be continued if chemotherapy is stopped because of toxicity or patient choice, but should be discontinued on recurrence or unacceptable Cetuximab toxicity. Full details of Cetuximab administration and dose reduction and delays are given in Appendix I.

9.c Surgery

The liver resection is carried out **at the earliest 4 weeks** after the last administration of chemotherapy and Cetuximab, and within 2 to 6 weeks of CT scanning at the end of the pre-operative period. Patients who progress during the first 12 weeks of chemotherapy and who are still operable should be considered for surgery. However these patients are unlikely to be salvaged with surgery and consideration should be given to second-line chemotherapy. In addition, the patient must have completely recovered from side effects, the general condition according to WHO grade must be ≤ 1 and liver function must be adequate for liver surgery.

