- **Progressive disease (PD):** $\geq 20\%$ increase in the sum of longest diameters of target lesions compared to smallest sum longest diameter recorded, or unequivocal progression of non-target lesions, or appearance of new lesions.

Reminder:

- Response is judged against baseline, but progression is judged against the smallest recorded score.

Example:

Month	0	3	6	9	12
Measurement (mm)	100	90	50	55	≥ 60
Classification	Baseline	SD	PR	PR	PD

References:

Gehan EA and Tefft MC. Will there be resistance to the RECIST (Response Evaluation Criteria in Solid Tumours)? J Natl Cancer Inst 2000, 92, 179-181.

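### The PFS assessment rule for resected patients leaves out progression before surgery, contradicting the general definition, so the primary event date can turn on a later decision to operate

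*Protocol*

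**What the plan says.** Protocol section 6 (Outcome measures, Definitions) opens with a general rule: "Progression-free survival (PFS) is defined as the time from randomisation to first recurrence/disease progression or death, whichever occurs first". It goes on to say "PFS will be assessed as follows", and splits patients by what happened at surgery.

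- **Resected.** "In patients with resected metastases (R0 or R1 or R2), PFS will be considered to be the time from randomisation" to the first of two events: "Recurrence/disease progression after surgery", or death.
- **Unresected.** The events are "Disease progression (whenever it occurs, before or after the planned surgery date"), or death.

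Section 9.c (Surgery) covers the patient on whom these rules disagree: "Patients who progress during the first 12 weeks of chemotherapy and who are still operable should be considered for surgery". It adds: "However these patients are unlikely to be salvaged with surgery and consideration should be given to second-line chemotherapy".

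Appendix V defines progressive disease by, among other criteria, a 20% or greater "increase in the sum of longest diameters of target lesions compared to smallest sum longest diameter recorded". A patient can meet this at the scan that ends the pre-operative period, which section 6 already requires for the response outcome. Section 18 compares the arms by intention to treat with Cox regression, and the title calls the trial open-label.

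**The concern.** The two lists cannot be read as equivalent. One expressly takes in progression on either side of the planned surgery date; the other is confined to progression after surgery. Two patients with the same scan showing progression would therefore get different primary event dates if one is then operated on and the other is not.

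That decision comes after randomisation and with the treatment arm known. Section 9.c presents it as a judgement, since it raises both surgery and second-line chemotherapy. Letting such a decision set the event date weakens a comparison that is meant to rest on randomisation alone. Nor can removal of the disease justify the rule throughout, because R2 patients are in the resected list.

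At stake is the dating of the primary endpoint. The hazard ratio could be biased if the arms differ in how many patients progress before surgery and are then resected.

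**Working it through.** **1. One patient under each rule.** Take a patient with RECIST progression at the pre-operative scan.

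| Rule in section 6 | Patient then resected | Patient not resected |
|---|---|---|
| General definition | Event at the scan | Event at the scan |
| Assessment lists | Event at later progression or death, otherwise censored | Event at the scan |

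Only one cell differs, so the problem is confined to patients who progress before surgery and are then resected. I found nothing in the protocol that reconciles the two rows.

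**2. The plan's own event target.** Section 18 gives HR 0.68, 80% power, 5% two-sided and 212 events. Schoenfeld's formula gives 4 × (1.960 + 0.842)² / (ln 0.68)² = 31.40 / 0.1487 = 211.1, rounded up to **212**. The target is reproduced. It depends only on the HR, alpha and power, so a change in how events are dated does not alter it.

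**3. How many patients could be affected.** Section 18 assumes 67% PFS at one year, a hazard of −ln 0.67 = 0.400 per year. Surgery is taken at weeks 16 to 20 (12 weeks of chemotherapy plus at least 4 weeks; the exact week is an assumption).

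- Control, week 16: 1 − exp(−0.400 × 16/52.18) = 11.6%. Week 20: 14.2%.
- Cetuximab at HR 0.68: 8.0% and 9.9%.
- Total with a PFS event before surgery: 134 × (0.116 + 0.080) ≈ 26, up to 134 × (0.142 + 0.099) ≈ 32, of 268.

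An exponential curve with section 18's other control figure, a 15-month median, gives 15.6–19.1% and 10.9–13.5%, or about 36 to 44 of 268. These are ceilings: they include early deaths, and only progressors who are later resected are re-dated. The protocol does not give that share.

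**4. Effect on the hazard ratio.** This was simulated with 134 per arm, an exponential control median of 15 months, surgery at month 4, 1,500 runs per setting, and every event before month 4 treated as a progression. The share of early progressors resected, and the median time from surgery to their next event (6 or 10 months), are assumptions. Pairs below are for 6 and 10 months. The last column is power when the true HR is 0.68, and one-sided false-benefit error (nominal 2.5%) when it is 1.00.

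| True HR | Resected, control / cetuximab | HR, general definition | HR, resected list | Power or error, general → list |
|---|---|---|---|---|
| 0.68 | 25% / 25% | 0.679, 0.681 | 0.680, 0.685 | 84.7→83.9%, 83.9→83.5% |
| 0.68 | 75% / 75% | 0.679, 0.681 | 0.685, 0.693 | 84.5→83.3%, 84.0→79.9% |
| 0.68 | 25% / 75% | 0.681, 0.680 | 0.662, 0.653 | 83.7→88.5%, 84.9→91.5% |
| 0.68 | 75% / 25% | 0.676, 0.680 | 0.702, 0.724 | 86.0→77.1%, 84.1→69.7% |
| 1.00 | 75% / 75% | 0.998, 0.997 | 0.998, 0.997 | 2.5→2.5%, 2.5→2.5% |
| 1.00 | 25% / 75% | 1.000, 0.998 | 0.955, 0.930 | 2.2→5.0%, 2.7→9.1% |
| 1.00 | 75% / 25% | 0.999, 1.009 | 1.046, 1.079 | 1.9→0.8%, 1.9→0.8% |

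With a milder contrast at true HR 0.68, 25% / 50% gives 0.679→0.670 and 0.681→0.669; 50% / 25% gives 0.675→0.689 and 0.675→0.699.

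**5. A second set of assumptions.** This uses section 18's curve of 67%, 46% and 35%, and sets directly the share of each arm that progresses at 3 months and is still resected. HRs are given as general definition, then resected list.

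- 10% against 3%, no other effect: 0.93, then 0.96–0.97.
- 3% against 8%, no other effect: 1.05–1.06, then 1.03.
- 10% against 3%, HR otherwise 0.68: 0.64, then 0.66.
- Similar shares in both arms: the two rules differ by about 0.01 at most.

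**6. Scale.** At 212 events the standard error of log HR is about 2/√212 = 0.137. The shift from 0.64 to 0.66 is ln(0.66/0.64) = 0.031, or 0.2 standard errors. The largest in the table, 0.998 to 0.930, is 0.071, or 0.5 standard errors.

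**The case against.** The strongest reply is that there is one definition and not two. The general sentence leads straight into the lists as the way PFS will be assessed, so on a normal reading the specific rule governs. The contrast in wording looks deliberate, and failure after resection is a coherent endpoint where resection is part of the planned strategy. This has force as an account of intent. But the lists do not carry out the sentence they serve, and a deliberate rule would still hang the event date on a decision made after randomisation. The strategy argument is weakest for R2 patients.

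Four stronger readings are tempting, and the protocol does not support them.

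- *That these patients have no event.* They are re-dated to a later progression or death, and censored only if neither occurs.
- *That pre-operative progression is dropped altogether.* It still counts for every unresected patient, and pre-operative response is a separate secondary outcome.
- *That this is classical immortal-time bias.* The comparison is between randomised arms, not resected against unresected patients. Bias between arms needs the arms to differ.
- *That about half of any pre-operative effect on the HR is lost.* That pattern comes from assumed contrasts such as 10% against 3%. The protocol's own curve with HR 0.68 implies about 11.6–14.2% against 8.0–9.9% having an event before surgery, a much milder ratio.

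It is also fair that section 9.c's doubt about the value of surgery in these patients suggests few would be affected, and that no passage supports a threefold difference between arms in willingness to operate.

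**Conclusion.** The defect stands on the text. For a patient who progresses before surgery and is then resected, section 6 gives two different primary event dates, and section 9.c shows that such patients were foreseen.

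Its numerical effect is probably small. If early progressors are resected about equally often in both arms, the HR moves from 0.68 to about 0.68–0.69, with at most a few points of power lost. A clear difference between arms is needed for a shift of about 0.02–0.04 at a true HR of 0.68, or about 0.05–0.07 at a true HR of 1.00. The direction is not known in advance. The 5–9% false-benefit error and the 70–77% power both rest on an assumed 25% against 75% split and should be quoted only as illustrations.

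The case for correction is that the primary event is inconsistently defined and depends on an open-label decision. It does not rest on any one hazard ratio, and a reader should not infer that the rule favours either arm.

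**What to change.** Replace the two lists in section 6 with one rule for all randomised patients: time from randomisation to the first RECIST progression or recurrence at any time, before or after surgery, or death from any cause, regardless of resection. This matches the general definition already there. If the rule confined to progression after surgery is wanted, keep it at most as a labelled sensitivity analysis.

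The 212-event target does not change. The scan at the end of pre-operative treatment is already required with RECIST assessment, so event dates can be re-derived from data already collected.

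The cost is more than editing a paragraph. Section 14 expected recruitment to end in December 2012, and the latest amendment listed in section 26 is dated October 2017. The change may therefore come after accrual. It needs a documented, justified amendment, agreed without sight of results by arm, and re-derivation of the affected dates.

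This takes no position on whether patients who progress should have surgery.

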Appendix VIII – Cockcroft & Gault formula	77
Appendix IX – EORTC QLQ questionnaires	78
Appendix X – EQ-5D questionnaire	83
Appendix XI – NCI common terminology criteria for adverse events (v3.0)	85
Appendix XII – Economic evaluation	87
Appendix XIII – Hypomagnesemia	90
Appendix XIV - New EPOC k-RAS Genotype Request Form	92

1. Trial design

2. Summary

Title	
	New EPOC: an open-label randomised trial, comparing OxMdG / IrMdG chemotherapy versus OxMdG / IrMdG chemotherapy plus Cetuximab.
Study population	
	Two hundred and eighty eight colorectal cancer patients with liver metastases deemed resectable in whom the oncologist feels chemotherapy would be beneficial, who are fit for combination chemotherapy, and possess the KRAS-wt genotype confirmed in primary tumour by laboratory analysis.
Study regimen	
	
Patients will be randomised at the start of chemotherapy to receive either:
 
Arm A: OxMdG / IrMdG chemotherapy
 
Arm B: OxMdG / IrMdG chemotherapy with Cetuximab
 
OxMdG: L-folinic acid (175 mg flat dose IV over 2 h) or d,L-folinic acid (350 mg flat dose IV over 2 h), concurrent administration of Oxaliplatin (85 mg/m² IV over 2 h) plus 5 minute bolus of 5FU (400 mg/m²) followed by a 46 h IV infusion of 5FU 2400 mg/m² repeated every 2 weeks as used in the FOCUS trial
 
or
 
IrMdG: Irinotecan 180 mg/m² IV over 30 minutes, L-folinic acid (175 mg flat dose IV over 2 h) or d,L-folinic acid (350 mg flat dose IV over 2 h) plus 5 minute bolus of 5FU (400 mg/m²) followed by a 46 h IV infusion of 5FU 2400 mg/m² repeated every 2 weeks as used in the FOCUS trial in patients intolerant of Oxaliplatin.
 
Cetuximab will be given as a fortnightly dose of 500 mg/m² with OxMdG and IrMdG. Patients will receive 12 weeks of chemotherapy, undergo surgery and then complete a further 12 weeks of chemotherapy.

Study objectives/endpoints	
	The primary endpoint is progression-free survival. Secondary endpoints include pre-operative response rate, overall survival, quality of life and cost effectiveness.
Supplementary studies	
	Patients will be asked for separate consent to use a blood sample and a proportion of their stored pathology samples for translational research projects. These include analyses of EGFR expression, biomarkers of response, DNA repair capacity and other pharmacogenomic studies.

3. Summary of interventions (treatment phase)

	Week ...																																				

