- DPD is the initial and rate-limiting enzyme for 5-FU breakdown. DPD deficiency is an inherited (pharmacogenetic) disorder in which individuals with absent or significantly decreased DPD activity develop life-threatening toxicity following exposure to 5-FU (in either IV or oral form). Reduced drug clearance results in markedly prolonged exposure to 5-FU so that administration of standard doses of 5-FU results in altered 5-FU pharmacokinetics and severe toxicity including mucositis, granulocytopenia, neuropathy

and death. The onset of toxicity usually occurs twice as fast in patients with low DPD activity as compared with patients with a normal DPD activity. Approximately 3-5% of the population has low DPD activity and 0.1% have absent activity. We recommend that (i) patients with a personal or family history suggestive of DPD deficiency should not be enrolled onto New EPOC, and (ii) those who experience grade 3/4 neutropenia and grade 3/4 mucositis after cycle 1 should be considered as potentially having DPD deficiency. If DPD deficiency is suspected, patients should only continue on trial after full recovery but without the further use of a Fluoropyrimidine.

- 5FU may provoke angina attacks or even MI in patients with ischaemic heart disease. Continued treatment with upgraded antianginal medication and reduced 5FU dose may be considered.

Cetuximab plus Oxaliplatin modified de Gramont administration

Patients will receive Cetuximab intravenous infusions at a dose of 500 mg/m² to be administered over 2 hours and thereafter fortnightly infusions. Cetuximab is provided in ready use vials containing 5 mg/ml. Once removed from the vial, Cetuximab must be used within 8 hours if stored at room temperature.

Please note Cetuximab must be administered under the supervision of a physician experienced in the use of antineoplastic medicinal products. Close monitoring is required during the infusion and for at least 1 hour after the end of the infusion. Availability of resuscitation equipment must be ensured. Vital signs should be checked and recorded before, during, and 1 hour after the Cetuximab infusion. There must be at least one hour between completion of the Cetuximab infusion and the start of chemotherapy.

Day 1 of treatment schedule (14 day cycle)

0:00	IV Chlorphenamine 10mg, Paracetamol 1g p.o., Ranitidine 150mg p.o. IV bolus DDexamethasone 8 mg IV bolus GGranisetron 3 mg (or equivalent) Flush line with 0.9% saline

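### The pre-operative delay clock starts at the end of chemotherapy and ignores cetuximab continued after it, so in some Arm B patients the interval passes 6 weeks with surgery on time

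*Protocol*

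**What the plan says.** Three parts of the protocol bear on this point.

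- **Section 6, Definitions** sets the event: "A pre-operative safety finding will be if >6 weeks delay of surgery due to study treatment-related toxicity". It then fixes the clock, "with the delay being measured between the end of pre-operative chemotherapy (last day of last cycle) and surgery". Cetuximab is not mentioned.
- **Section 9.b**, for Arm B: "Cetuximab will be continued if chemotherapy is stopped because of toxicity or patient choice, but should be discontinued on recurrence or unacceptable Cetuximab toxicity".
- **Section 9.c**: "The liver resection is carried out at the earliest 4 weeks after the last administration of chemotherapy and Cetuximab".

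Elsewhere section 6 uses wider terms. Pre-operative response is timed from the end of the pre-operative treatment period, and the 8-week post-operative delay runs to the start of post-operative study treatment. Only the pre-operative delay clock is tied to chemotherapy.

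**The concern.** In Arm A the end of chemotherapy is also the end of pre-operative treatment, so the clock and the surgery rule start together. In Arm B they can separate: chemotherapy stops for toxicity and starts the clock, while cetuximab continues and keeps surgery from being permitted. The interval then includes weeks of planned treatment and the mandatory wait after cetuximab, in which surgery is not late at all.

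What is at stake is how this safety finding reads in the experimental arm. In such a patient a short postponement, far below 6 weeks, would be recorded as a delay of more than 6 weeks. The trial is also open-label, so someone who knows the allocation could attribute the long interval to the toxicity that stopped chemotherapy. Both errors run against cetuximab.

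**Working it through.** The protocol states no figure to reproduce here. The check is calendar arithmetic.

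**Inputs**
- Pre-operative treatment lasts 12 weeks (section 2: "Patients will receive 12 weeks of chemotherapy, undergo surgery and then complete a further 12 weeks of chemotherapy").
- Cycles last 14 days, with cetuximab on day 1 and the 5FU infusion ending on day 3 (Appendix I). This gives 84 / 14 = 6 cycles.
- Surgery is at least 28 days after the last dose of both treatments (section 9.c).
- The limit is 6 x 7 = 42 days (section 6).
- Assumption: cetuximab continues to cycle 6. The protocol gives no separate pre-operative stop for cetuximab alone, apart from recurrence or unacceptable cetuximab toxicity.

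**Formulas**, with day 1 as the start of treatment and chemotherapy ending after cycle k:
- The last day of cycle k is day 14k.
- The last cetuximab dose is on day 14 x 5 + 1 = 71.
- Arm B, k = 1 to 5: earliest surgery is day 71 + 28 = 99, so the interval is 99 - 14k.
- Arm B, k = 6: 5FU ends on day 73, so earliest surgery is day 101 and the interval is 101 - 84 = 17.
- Arm A, any k: 5FU ends on day 14(k - 1) + 3. Earliest surgery is 28 days later, so the interval is 14(k - 1) + 31 - 14k = 17.

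The last day of the cycle could also be read as pump disconnection on day 3. The Arm B interval is then 99 - [14(k - 1) + 3] = 110 - 14k for k = 1 to 5, and 101 - 73 = 28 for k = 6. In Arm A it is 28 throughout.

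| Chemotherapy ends after cycle | Arm B shortest interval, day-14 reading | Arm B shortest interval, day-3 reading | Above 42 days? |
|---|---|---|---|
| 6 | 17 | 28 | no |
| 5 | 29 | 40 | no |
| 4 | 43 | 54 | yes |
| 3 | 57 | 68 | yes |
| 2 | 71 | 82 | yes |
| 1 | 85 | 96 | yes |

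On both readings the shortest permitted interval passes the limit once at least two cetuximab-only cycles follow the last chemotherapy cycle.

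**Effect on a genuine short delay** (day-14 reading). A patient who completes six cycles has 42 - 17 = 25 days of slack after the first permitted day. A patient whose chemotherapy ended after cycle 4 has 42 - 43 = -1. If toxicity moves that patient's surgery by one week, from day 99 to day 106, the recorded delay is 106 - 56 = 50 days and the finding is met. Counted from the end of cycle 6, the same surgery gives 106 - 84 = 22 days.

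**The case against.** **The toxicity condition.** A reader might infer that these Arm B patients meet the finding automatically. They do not. The delay of surgery itself must be due to toxicity. A patient who stopped chemotherapy by choice is not counted on the length of the interval alone, and a patient operated on at day 99 has not had surgery put off. The cause of stopping chemotherapy is not the cause of delaying surgery. This stands, and it rules out the stronger reading. It does not repair the clock: once there is any toxicity-related postponement, however short, the condition is met and the length is measured from the wrong day.

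**Chemotherapy may include cetuximab.** The schedule table in section 3 labels cetuximab as a chemotherapy item, and Appendix I lists the cetuximab combinations among the chemotherapy regimens. On that reading the last cycle is the last cetuximab cycle and the problem disappears. However, sections 9.b and 9.c name the two separately, and the administration notes in Appendix I require a gap between cetuximab and the start of chemotherapy. The label does not settle the meaning, and clarifying it needs the same correction.

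**Arm A can also pass 6 weeks.** This is true. If an Arm A patient stops early and surgery is still held on day 99, the intervals are the same 43 to 85 days. Nothing in the protocol forces that, whereas in Arm B the wait after cetuximab is required. The first permitted day is also not the expected day in either arm, since section 9.c asks for full recovery first.

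**Size and use.** A reader might want a count of spurious Arm B events. The protocol gives no rate for stopping all chemotherapy while continuing cetuximab, so none can be derived. The path is narrow. For the cumulative toxicity that section 9.b calls most likely, oxaliplatin neuropathy rising from about 12 weeks, 5FU may continue and the clock is unaffected. Nor does section 18 state a comparison of this finding between arms; the outcome list in section 6 names peri-operative safety findings, not this one.

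**Conclusion.** The point holds as a minor mismatch in an outcome definition. Section 6 and sections 9.b and 9.c use different reference points in Arm B. With at least two cetuximab-only cycles before surgery, the measured interval exceeds 42 days even with surgery on the first permitted day: by 1, 15, 29 or 43 days for a stop after cycle 4, 3, 2 or 1. This rests on cetuximab running to cycle 6 and on the cycle ending on day 14; the day-3 reading gives larger excesses.

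The consequence is that a short toxicity-related postponement, or an unblinded attribution to the toxicity that stopped chemotherapy, can be recorded as a delay of more than 6 weeks. The documents do not support calling the event automatic or putting a number on affected patients.

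**What to change.** In section 6, count the delay from the last day of the last pre-operative cycle of any study treatment, chemotherapy or cetuximab. State what the last day of a cycle means, since a cetuximab-only cycle has no pump disconnection. This reconciles section 6 with sections 9.b and 9.c.

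Keep the end of the cycle as the anchor. Moving it to the last administration may look simpler, but it would tighten the limit for everyone. A patient completing six cycles now passes it after day 84 + 42 = 126. From the last administration that becomes day 71 + 42 = 113 or day 73 + 42 = 115, depending on whether the day-1 infusion or the end of 5FU is used. That is 13 or 11 days earlier. With the cycle-end anchor, nothing changes for patients who complete all cycles.

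The cost is one phrase. Section 11.e already records cetuximab administration at each cycle, so no new data are needed. The small downside is that early stopping of chemotherapy with cetuximab continued no longer lengthens this interval, so it should be reported separately by arm. No treatment or surgery-timing rule changes.
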